The study will end for subjects when they have completed the second follow-up visit scheduled 25 (\pm 4) days after the final day 7 visit, or at the time they chose to withdraw from the study or are removed from the study by decision of the principle investigator.

VI. Subject Selection

VI.a. Inclusion Criteria

Subjects

1. Age \geq 18 years and have had clinical type 1 diabetes for at least one year
2. Diabetes managed using an insulin pump for \geq 3 months
3. Prescription medication regimen stable for $>$ 1 month (except for medications that will not affect the safety of the participant and are not expected to affect any outcome of the study, in the judgement of the principal investigator)
4. Willing to wear one Dexcom CGM sensor, and up to two steel cannula infusion sets (6 mm Contact Detach) and change infusion sets frequently (if the subject is known not to tolerate steel infusion sets then a plastic set may be used)
5. Have used a CGM for at least one cumulative month over the last 24 months
6. Willing to stay within a 250-mile radius of the designated base throughout the study. Air travel is not permitted.
7. Informed consent obtained before any trial-related activities
8. Have a designated contact (an adult \geq 18 years of age) willing to serve as an emergency contact for them throughout the study.

Designated Contacts

1. Age \geq 18 years
2. Have an established relationship with the study participant
3. Willing to answer questionnaires about their experience with the participant's diabetes and the bionic pancreas
4. Willing to answer calls and check on the participant's wellbeing as needed
5. Able to provide informed consent (e.g. no condition that impairs cognition or judgement)

VI.b. Exclusion Criteria

1. Unable to provide informed consent (e.g. impaired cognition or judgment)
2. Unable to safely comply with study procedures and reporting requirements (e.g. impairment of vision or dexterity that prevents safe operation of the iLet, impaired memory, unable to speak and read English)
3. Current participation in another clinical trial with administration of investigational drug.
4. Current participation in another diabetes-related clinical trial that, in the judgment of the principal investigator, will compromise the results of this study or the safety of the participant
5. Previous exposure to dasiglucagon (otherwise known as ZP4207)

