- Study staff will review all study procedures and policies (including the use of the Dexcom G5, the Contour Next One, and the iLet) and the upcoming visit schedule.
- The control algorithm will be initialized with the participant's current weight. The participant will set up and start the iLet under the supervision of study staff. Participants will be instructed to not take any further insulin outside of the iLet throughout the study.
- The staff will confirm that the iLet is functioning properly prior to discharging the participant.
- All participants will be given additional supplies as needed.

Final Day 7 Visit:

- At the end of the second 7-day arm, subjects will return to the clinic and answer the post questionnaires for the study arm.
- The body weight, heart rate and blood pressure of the subject will be documented.
- Blood will be drawn for a chemistry panel and complete blood count.
- An EKG will be performed. This EKG will be assessed relative to the baseline EKG to identify any potential changes.
- Any changes to medications or medical history and any adverse events that may have occurred since their last study visit will be documented. Study staff will specifically ask subjects if they had any infusion site reactions or other skin irritation in the past 7 days, and will document any reactions.
- The iLet and the study meters will be downloaded.
- All equipment will be collected and cleaned. The Dexcom G5 transmitter will be cleaned using the validated cleaning and disinfecting procedures.
- A study provider will review the last few hours of glucose trend data and insulin and dasiglucagon on board from the iLet, and assist the participants in resuming their usual diabetes management.

Follow Up Visits

- Subjects will return for a follow up visit 10 days (± 3 days) after the final day 7.
 - Any changes to medications or medical history and any adverse events that may have occurred since their last study visit will be documented. Study staff will specifically ask subjects if they had any infusion site reactions or other skin irritation since their last study visit, and will document any reactions.
 - Blood will be drawn for anti-drug antibodies.
 - If the EKG on the final Day 7 visit showed any changes relative to the baseline EKG, an additional EKG will be performed at this follow up visit.
- Subjects will return for a second follow up visit 25 days (± 4 days) after the final day 7.

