 - Any changes to medications or medical history and any adverse events that may have occurred since their last study visit will be documented. Study staff will specifically ask subjects if they had any infusion site reactions or other skin irritation since their last study visit, and will document any reactions.
 - Blood will be drawn for a chemistry panel, complete blood count, and anti-drug antibodies.

VI. d. v. Response to Hypoglycemia

- The response to hypoglycemia will be the same in both arms. Subjects will be reminded that the iLet decreases insulin dosing in response to decreasing CGMG in both the insulin-only and bihormonal configurations.

- The Dexcom G5 app will generate a local low glucose threshold alarm if the subject's CGM value is ≤ 70 mg/dl and the iLet will generate an alarm for a CGMG < 50 mg/dl.
- In all study arms subjects are encouraged to check their BG for any symptoms of hypoglycemia.
- Subjects are encouraged to treat hypoglycemia according their usual practice or according to the "rule of 15s": take 15 grams of rapid acting carbohydrate and recheck in 15 minutes, then repeat as needed. Subjects will be reminded to check their glucagon infusion site and their bionic pancreas for normal operation anytime they experience hypoglycemia during the bihormonal arm. If there is any suspicion of glucagon infusion set malfunction, the site should be replaced.
- Subjects may contact a study provider (RN, MD or NP) for advice at any time, and may contact the troubleshooting support team, as they wish. Subjects will be assisted in checking the bionic pancreas for any malfunction and correcting any problems that are found.
 - If no correctable fault is found, but there is doubt regarding the correct function of the bionic pancreas system, an entirely new backup bionic pancreas system may be brought to the subject's location by study staff.
- If a subject experiences severe hypoglycemia in the study, his or her participation in the study will be discontinued.

VI. d. vi. Response to Hyperglycemia

- The response to hyperglycemia will be the same in both arms.
- The Dexcom G5 app will generate a local high glucose threshold alarm if the subject's CGM value is > 250 mg/dl. Subjects will be instructed to check their insulin infusion site and their bionic pancreas for normal operation any time they get this alarm, or BG is greater than 250 mg/dl. If there is any suspicion of insulin infusion set malfunction, the site should be replaced.

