There is a risk of headache, nausea or vomiting due to the administration of exogenous glucagon. There is a possible risk of skin rash due to administration of exogenous glucagon. There may be risks of daily, low-level glucagon administration that have not become apparent during trials lasting up to 11 days. Possible risks include changes in body weight, blood pressure or blood chemistries or blood counts, or development of anti-drug antibodies. The magnitude of the other possible risks due to daily administration of small amounts of glucagon are unknown, but are not expected to be high because mean glucagon levels have been in the fasted range in previous trials. Of note, the risk of nausea and vomiting has been low in prior studies. There may be other unknown risks associated with dasiglucagon.

IX. Potential Benefits

It is expected that this protocol will yield increased knowledge about using an automated closed-loop to control the glucose level. This research is one step on the path towards development of a fully closed-loop system, and is particularly important for establishing the safety and efficacy of a bihormonal system for larger and longer future studies. The individual participant may not benefit from study participation.

Based on evidence from previous trials of the bionic pancreas and the design of this trial, subjects enrolled in the study may benefit from a reduction in risk of hypoglycemia and hyperglycemia and a better mean glucose than they typically achieve.

Subjects will be financially compensated for participating in the study.

X. Data and Safety Monitoring

X. a. Monitoring of Source Data

During the experiment, CGM data, insulin dosing data, and glucagon dosing data will be automatically stored in the bionic pancreas device (from which it will be downloaded at intervals). All of the data will be combined in a single database that will be compared against the primary data files for integrity. The computer database will be backed up at least monthly and the backup media stored in a secure location.

Study staff will be encouraged to raise any concerns they may have or problems they have identified at any time. The PI, in consultation with the co-investigators, will decide a course of corrective action, and resolution or progress will be assessed no later than the next meeting.

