The participation of individual subjects in the study will be discontinued if:

- Subjects experience one episode of diabetic ketoacidosis (DKA) requiring hospitalization
 - Hyperglycemic events will be classified as DKA if the following are present:
 - Symptoms including but not limited to polyuria, polydipsia, nausea or vomiting
 - Serum ketones > 1.5 mmol/L or large/moderate urine ketones
 - Either arterial blood pH <7.30 or venous pH < 7.24, or serum bicarbonate < 15
 - Treatment provided in a healthcare facility
- Subjects experience one episode of severe hypoglycemia, defined as requiring the assistance of

another person due to altered consciousness, and required another person to actively administer carbohydrate, glucagon or other resuscitative actions. This means the participant was impaired cognitively to the point that he/she was unable to treat himself/herself, was unable to verbalize his/her needs, was incoherent, disoriented, and/or combative, or experienced seizure or coma. If plasma glucose measurements are not available during such an event, neurological recovery attributable to the restoration of plasma glucose to normal is sufficient evidence that the event was induced by a low plasma glucose concentration.

- Subjects experience persistent nausea and vomiting thought to be related to glucagon dosing in the bi-hormonal bionic pancreas arm
- The investigator believes it is unsafe for the participant to continue in the study
- A participant becomes pregnant
- The participant requests that the study be stopped

If more than 1 subject must be withdrawn from the study for severe hypoglycemia or DKA, the study will stop and a vote of the DSMB will be required to restart it. All serious and unexpected events will be reported to the DSMB within 72 hours.

Study participation is voluntary, and participants may withdraw at any time. The investigator may withdraw a participant who is not complying with the protocol. For participants who withdraw, their data will be used up until the time of withdrawal. For participants using the iLet who withdraw, a study provider will help them transition to their own therapy safely.

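### A dasiglucagon-exposed subject who stops before the final Day 7 has no scheduled antibody sample, EKG or follow-up adverse-event review, because withdrawal or removal ends the study and both follow-up visits are dated from that day

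*Combined protocol and SAP*

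**What the plan says.** Section III.c gives a subject two ways to end the study: completing the second follow-up visit, or leaving earlier, in which case the study ends "at the time they chose to withdraw from the study or are removed from the study by decision of the principle investigator".

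The safety stops are worded as the end of participation, not of treatment alone. The list in X.b opens "The participation of individual subjects in the study will be discontinued if" and covers DKA requiring hospitalization, severe hypoglycemia, persistent nausea and vomiting attributed to glucagon, investigator safety concern, pregnancy and participant request. VI.d.v repeats it for one trigger: "If a subject experiences severe hypoglycemia in the study, his or her participation in the study will be discontinued". VI.d.vi and VI.d.vii do the same for DKA and for nausea and vomiting.

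The visit schedule in VI.d.iv hangs on one date. The Final Day 7 visit is defined by "At the end of the second 7-day arm, subjects will return to the clinic and answer the post questionnaires for the study arm". The follow-up visits are then set by "Subjects will return for a follow up visit 10 days (± 3 days) after the final day 7" and "Subjects will return for a second follow up visit 25 days (± 4 days) after the final day 7".

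For subjects who leave early, VI.d.iii and X.b provide help in returning to usual therapy, and X.b adds: "For participants who withdraw, their data will be used up until the time of withdrawal". Section VIII states what might be found with repeated glucagon dosing: "Possible risks include changes in body weight, blood pressure or blood chemistries or blood counts, or development of anti-drug antibodies".

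**The concern.** Read together, these rules make late safety data conditional on completion. Completion is not independent of safety here, because several reasons for stopping are suspected harm from the drug or device. The subjects most informative about tolerability are those for whom the antibody, EKG and late adverse-event assessments are not scheduled.

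Safety is a stated aim of the study, and subjects with earlier dasiglucagon exposure are excluded. The longest dasiglucagon exposure whose results the protocol describes is an in-clinic session of up to 8 hours (I.e and VI.b), whereas each subject here is to have a 7-day arm. The treatment-emergent definition in VII.d.iv has a start and no end, so a late event in a stopped subject would count, but nobody is scheduled to ask about it. X.b also pauses the study for a DSMB vote if more than one subject is withdrawn for severe hypoglycemia or DKA. That vote could be taken without scheduled post-event laboratory, EKG or antibody results from those subjects.

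**Working it through.** The plan gives no figure to reproduce; the check is a trace of each safety assessment to its visit, and of each visit to its anchor date.

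**Inputs (VI.d.iv, confirmed for the EKG in VII.e.ii)**

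- Antibodies: baseline at Day 1, then follow-up 1 and follow-up 2 only.
- EKG: screening, then Final Day 7. It is repeated at follow-up 1 only if the Final Day 7 tracing has changed.
- Chemistry and CBC: Day 1, Day 7/Day 1, Final Day 7, follow-up 2.
- Adverse-event review after Day 1: Day 7/Day 1, Final Day 7, follow-up 1, follow-up 2.
- Anchors: Day 7/Day 1 is the end of the first arm and Final Day 7 the end of the second. Follow-up 1 is 7 to 13 days after Final Day 7, and follow-up 2 is 21 to 29 days after it.

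**Assessments scheduled after dasiglucagon exposure has begun**

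| Assessment | Completer, bihormonal first | Completer, bihormonal second | Stopped during bihormonal arm (either order) | Stopped in arm 2 after bihormonal arm 1 |
|---|---|---|---|---|
| Antibody samples | 2 | 2 | 0 | 0 |
| Unconditional EKG | 1 | 1 | 0 | 0 |
| Chemistry and CBC | 3 | 2 | 0 | 1 |
| Adverse-event review at a visit | 4 | 3 | 0 | 1 |

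In the fourth column, when the bihormonal arm comes second, the Day 7/Day 1 blood draw precedes dasiglucagon and so does not count. In the last column, the single entries are the Day 7/Day 1 assessments. A subject stopped in a first, insulin-only arm was never exposed and is outside the table.

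**Is there an unlisted termination visit?** Section XI pays $25 for screening and $50 for each of five study visits: 25 + 5 × 50 = $275, the stated total. The five are Day 1, Day 7/Day 1, Final Day 7 and the two follow-ups, so no sixth visit is hidden there.

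**Effect on precision.** Assume 10 exposed subjects, no antibody-positive result, and a one-sided 95% upper bound of 1 − 0.05^(1/n):

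- all 10 sampled: 25.9%
- 9 sampled: 28.3%
- 8 sampled: 31.2%

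Each subject lost from 10 removes 10% of these data, but the bound moves only modestly. If stopped subjects are replaced (V.a allows up to 20 enrolled for 10 completers), the bound stays at 25.9% but describes completers alone. The main loss is therefore selection, not precision.

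**The case against.** The strongest reply is that safety capture does not stop with the subject. The event that causes a stop is itself an adverse event or a listed safety endpoint. Reasons for discontinuation are tabulated (VII.d.v), investigators review adverse events after each experiment (X.c), serious events go to the DSMB (X.b), and nausea and vomiting are solicited daily during the arms (VI.d.iii). Antibodies and EKG are not listed endpoints. All of this stands. A reader might infer that the whole safety summary is biased toward tolerability, or that stopped subjects have no post-exposure safety data. The documents support neither, and the last column of the table contradicts the second. The provisions above do, however, handle events already known; none is a scheduled contact or sample after the stop.

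Nothing forbids a site from drawing the sample or recording the EKG. That is right too, which is why the finding is that these assessments are not scheduled, rather than that they will not happen.

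It can also be said that III.c speaks of withdrawal or an investigator's decision, and X.b's data sentence of participants who withdraw, so neither need cover an automatic safety stop. The wording is loose enough for that reading. But no third status is defined, and even on that reading the follow-up visits have no date when there is no final Day 7.

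Finally, a reader might infer from the birth-defect criterion in the serious-event list (X.c) that pregnancies should be followed to outcome. The end-of-study rule does not lead there. Completers also leave about 25 days after the final Day 7, and the list is a general definition.

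**Conclusion.** The point holds for subjects who have received dasiglucagon and stop before the final Day 7. For them, the plan schedules 0 of 2 antibody samples, 0 of 1 unconditional EKGs and 0 of 2 follow-up adverse-event reviews. Post-exposure chemistry and CBC are also unscheduled if the stop falls in the bihormonal arm. Antibody, EKG and late adverse-event results would then describe completers only, although section VIII names antibodies as a possible risk.

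The conclusion assumes that sites follow the text as written. The number of such subjects cannot be derived from the documents: V.a explains the enrolment ceiling by screening exclusions and discontinued experiments generally, not by safety stops. The primary operational endpoint is unaffected. This should be corrected, but it does not threaten the main purpose of the study.

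**What to change.** Reconcile III.c, VI.d.iv and X.b so that stopping study treatment is a separate status from leaving the study. For dasiglucagon-exposed subjects who stop early, unless they withdraw consent to follow-up:

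1. Perform the existing Final Day 7 safety assessments (adverse-event review, chemistry, CBC, EKG) at the stop.
2. Keep the existing 10-day and 25-day visits, with their present content and windows, dated from the last use of the study device.
3. In X.b, limit the sentence on using data up to withdrawal to subjects who withdraw consent.

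This anchor does not distort antibody timing. In completers, the nominal gap from last dasiglucagon to follow-up 1 is 10 days if the bihormonal arm is second. If it is first, the gap is 10 + 7 = 17 days with no washout, and 10 + 7 + 7 = 24 days with the longest. Early stoppers would fall within the same 10 to 24 days.

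The cost is amendment wording plus up to three existing visits per exposed early stopper: at most 3 × ($50 + $30 parking) = $240. Total compensation would be $25 + $50 + 3 × $50 = $225 after a stop in the first arm and $25 + 2 × $50 + 3 × $50 = $275 after a stop in the second, so no more than for a completer. XI currently prorates payment to visits completed, so the sponsor should confirm funding. Some subjects will decline to return, and the number who do should be reported.

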6. Pregnant (positive urine HCG), breast feeding, plan to become pregnant in the next 12 months, or sexually active without use of contraception
 - a. Subjects must use acceptable contraception for the two weeks prior to the study, throughout the study and for the two weeks following the study.
 - b. Acceptable contraception methods include:
 - Oral contraceptive pills (OCP)
 - Intrauterine Device (IUD, hormonal or copper)
 - Male condoms
 - Female condoms
 - Diaphragm or cervical cap with spermicide
 - Contraceptive patch (such as OrthoEvra)
 - Contraceptive implant (such as Implanon, Nexplanon)
 - Vaginal ring (such as Nuvaring)
 - Progestin shot (such as Depo-Provera)
 - Male partner with a vasectomy proven to be effective by semen analysis
7. Current alcohol abuse (intake averaging >4 drinks daily in last 30 days) or other substance abuse (use within the last 3 months of controlled substances other than marijuana without a prescription)
8. Unwilling or unable or to avoid use of drugs that may dull the sensorium, reduce sensitivity to symptoms of hypoglycemia, or hinder decision making during the period of participation in the study (use of benzodiazepines or narcotics, even if by prescription, may be excluded according to the judgment of the principal investigator)
9. Renal failure on dialysis
10. History of cystic fibrosis, pancreatitis, or other pancreatic disease, including pancreatic tumor or insulinoma, or history of complete pancreatectomy
11. Coronary artery disease that is not stable with medical management, including unstable angina, angina that prevents moderate exercise (e.g. exercise of intensity up to 6 METS) despite medical management, or within the last 12 months before screening a history of myocardial infarction, percutaneous coronary intervention, enzymatic lysis of a presumed coronary occlusion, or coronary artery bypass grafting
12. Abnormal EKG consistent with increased risk of malignant arrhythmia including, but not limited

to, evidence of active ischemia, proximal LAD critical stenosis (Wellen's sign), or prolonged QT interval (QTc > 500 ms). Other EKG findings, including stable Q waves, are not grounds for exclusion as long as the participant is not excluded according to other criteria. A reassuring evaluation by a cardiologist after an abnormal EKG finding may allow participation.

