- A urine pregnancy test will be performed in pre-menopausal female volunteers. If the test is positive the volunteer will be informed of the result and the visit will be ended.
- Height, weight, heart rate and blood pressure will be measured. An EKG will be performed.
- If the volunteer is not excluded based on historical criteria, blood pressure, EKG or urine pregnancy test, blood will be drawn for hemoglobin A1c, and fractionated metanephrines if applicable. A study MD or NP will review the case report form to determine subject eligibility. If subjects are not eligible to continue in the study the results of abnormal tests will be reported to the subjects and to a health care provider of their choosing.
- A questionnaire will be administered to assess impaired awareness of hypoglycemia.
- Subjects who have been screened and are eligible can participate without having to be re-screened for a period of 3 months. The study staff should verbally confirm that there have been no health events that would make them ineligible at every study visit, and rescreen subjects for eligibility if it has been greater than three months.
- Once enrolled, subjects will identify up to 2 designated contacts (caregivers/family

members/friends) who are willing to serve as an emergency contact for the participant, requiring them to answer phone calls and check on the participants wellbeing as needed. If possible, they would also be an appropriate person to answer questionnaires about their experiences and attitudes towards the subject's diabetes and the impact of the bionic pancreas.

- Study staff will confirm the designated contacts are able to provide informed consent and are willing and able to serve as an emergency contact, and can recognize and treat hypoglycemia. If possible, they will confirm the contacts also have an appropriate relationship with the study participants to answer these questionnaires. Informed consent will be obtained from these contacts, and study staff will collect basic demographic information (age, sex, race/ethnicity) as well as contact information.
- All designated contacts will be trained in the symptoms of hypoglycemia and response to severe hypoglycemia, including the administration of glucagon. They will also be trained to recognize the symptoms of hyperglycemia, and when to contact study staff and local EMS.

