 - Study staff will verify the participants are aware of the hypoglycemia and taking action to treat it. Participants will be reminded of the protocol for hypoglycemia, and the study provider will ensure they understand and will follow study procedures. Participants will be encouraged to follow up with any questions or concerns. All contact with the participants in response to hypoglycemia alarms will be documented.
 - In the case of a low threshold alarm with no response from the participant and no success in locating them or their designated contact, the site principal investigator will be immediately informed. If remote monitoring shows ongoing hypoglycemia, a decision may be made to dispatch emergency medical services to the locations the participant is known to frequent.
 - Remote monitoring for hypoglycemia will be the same in both study periods.
- The remote monitoring system will generate an alarm if the CGM glucose is > 300 mg/dl for 90 minutes.
 - Participants will be reminded of the protocol for prolonged hyperglycemia, and the study provider will ensure they understand and will follow study procedures. Participants will be encouraged to follow up with any questions or concerns. All contact with the participants in response to hyperglycemia alarms will be documented.

- Remote monitoring for hyperglycemia will be the same in both study periods.

VI. d. iv. Visit Procedures

Day 1 Visit:

Participants may be trained on the operation of the all study devices in a group setting or may be trained one-on-one. Both the participant and the study staff must be satisfied that the participant is comfortable with the operation of all study devices before he/she begins the study. Additional training sessions may be arranged as needed.

- Participants will complete their baseline psychosocial questionnaires
- Their body weight, heart rate and blood pressure will be documented
- Blood will be drawn for a chemistry panel and complete blood count, and a baseline assessment of anti-drug antibodies.
- Study staff will review any changes in the participant's medical history or medications to ensure continued eligibility, and any adverse events that may have occurred since their screening visit. Study staff will specifically ask subjects if they had any infusion site reactions or other skin irritation in the past 7 days, and will document any reactions.

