No inferential tests of safety data will be performed. Descriptive summaries of safety data will be presented. Adverse events (treatment-emergent unless otherwise specified) will be presented by system organ class (SOC) and preferred term (PT) for each treatment group. Treatment-emergent AEs are defined as AEs with onset date on or after the first day of exposure to randomized treatment.

VII.d.v Baseline Descriptive Statistics

The number and percentage of patients who were screened, randomized, discontinued (with reason for discontinuation), and completed the trial will be summarized descriptively for all screened patients.

VII.d.viii Tabulation of Individual participant Data

Listings of individual patient data will be presented.

VII.d.ix Exploratory Analyses

The performance of the iLet in each period can be compared with historical data from previous bionic pancreas trials using previous generations of hardware. If the performance of the iLet in this study is

comparable to our previous data from trials using the iPhone-based bionic pancreas that will support the hypothesis that both configurations of the iLet are effective and safe implementations of the bionic pancreas. All participants with at least 24 hours of CGM data during days 2-7 of any treatments periods will be included in these analyses.

We may, in exploratory analyses, also stratify subjects for secondary analyses of the pre-specified endpoints by subject characteristics including: sex, age, baseline A1c, usual care insulin total daily dose, body mass index, phase of menstrual cycle (follicular vs. luteal).

VII. e Data Collected

VII. e. i. Prior to the start of the experiment:

- Age
- Sex
- Race and ethnicity
- Date of last menstrual period in female subjects
- Date of diabetes diagnosis
- Medical, surgical, and social history, allergies, and review of systems relevant to inclusion and exclusion criteria
- Medications (prescription and non-prescription) and date of last change in medication regimen
- Duration of insulin pump use
- Type of insulin used in pump
- Average total daily dose of insulin in the last 30 days as available
- Usage of CGM (type of CGM, days per month worn, usage of data, whether insulin is dosed based on CGM alone, alarm settings)
- Height and weight
- Blood pressure
- Heart rate
- EKG
- Hemoglobin A1c
- Fractionated metanephrines, if applicable
- Urine HCG (pre-menopausal females)

VII. e. ii. During study arms

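### The only scheduled pregnancy test is at screening, which stays valid for 3 months; none is listed at the start of either arm, so an unrecognised pregnancy could be missed before dasiglucagon

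*Combined protocol and SAP*

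**What the plan says.** All references are to the combined protocol and SAP.

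- **Definition.** VI.b. Exclusion Criteria, criterion 6, excludes: "Pregnant (positive urine HCG), breast feeding, plan to become pregnant in the next 12 months, or sexually active without use of contraception". Sub-item 6a adds: "Subjects must use acceptable contraception for the two weeks prior to the study, throughout the study and for the two weeks following the study".
- **The test.** VI. d. i. Screening Visit: "A urine pregnancy test will be performed in pre-menopausal female volunteers". A positive result ends the visit. Urine HCG also appears in VI. a. Screening Data and in VII. e. i, the list of data collected before the experiment starts.
- **How long screening lasts.** VI. d. i: "Subjects who have been screened and are eligible can participate without having to be re-screened for a period of 3 months". The next sentence gives the check in the interval: "The study staff should verbally confirm that there have been no health events that would make them ineligible at every study visit". It adds re-screening once more than three months have passed.
- **Later visits.** In VI. d. iv. Visit Procedures, the Day 1 laboratory work is: "Blood will be drawn for a chemistry panel and complete blood count, and a baseline assessment of anti-drug antibodies". The crossover and final Day 7 visits have a chemistry panel and blood count. The follow-up visits have anti-drug antibodies, with chemistry and blood count at the second. None of these lists an HCG, and VII. e. ii (data collected during the arms) has none either.
- **Discontinuation.** X. b. Safety Monitoring includes among the reasons to stop a subject's participation: "A participant becomes pregnant".

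**The concern.** The plan does not rely on history alone to establish that a woman is not pregnant. It makes a laboratory result the criterion and carries out the test. Up to three months later, when the investigational drug is about to be given, it relies on conversation and record review, and these cannot find a pregnancy the woman is unaware of. The exclusion is therefore verified by test at screening but not at the point of exposure.

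What is at stake is exposure to dasiglucagon in pregnancy. The drug is being used under an IND, and VIII. Risks and Discomforts accepts that it may carry risks not yet known. This is a point about safety and eligibility; it changes no sample size, power or analysis.

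**Working it through.** The plan gives no figure to reproduce. The check is a search of the visit lists followed by day counts.

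**1. Where a pregnancy test is listed**

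| Place in the protocol | HCG listed? | Other check bearing on pregnancy |
|---|---|---|
| VI. a. Screening Data; VI. d. i; VII. e. i | Yes, urine | Date of last menstrual period |
| VI. d. iv, Day 1 | No | Review of history, medications and adverse events; verbal confirmation |
| VI. d. iv, Day 7/Day 1 | No | Same |
| VI. d. iv, Final Day 7 | No | Changes in history and medications, adverse events |
| VI. d. iv, both follow-up visits | No | Same |
| VII. e. ii, during the arms | No | None listed |

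**2. From the test to the first start of the iLet**

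Three calendar months are 89 to 92 days, depending on the months. This is the longest interval allowed. The documents give no expected interval.

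**3. From the test to the first dasiglucagon**

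- Bihormonal arm first: up to 89 to 92 days.
- Bihormonal arm second: add the 7-day first arm and a washout of 0 to 7 days, that is 7 to 14 days. The shortest case is 89 + 7 = 96 days and the longest is 92 + 14 = 106 days.

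The second range applies only if the three-month limit is not applied again at the crossover visit. The sentence on re-screening can be read either way, and it does not say whether re-screening repeats the HCG.

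**4. The contraception window**

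6a counts two weeks back from the study without saying which event begins the study.

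- If it means Day 1: 89 − 14 = 75 to 92 − 14 = 78 days can follow the test before the dated requirement in 6a begins.
- If it means screening: 0 days.

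The absence of a repeat test is the same on both readings, so the main point does not depend on this one.

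**5. How many women**

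V. a. expects 10 completers, and VI. c. Sources of Subjects anticipates equal numbers of men and women: 10 × 0.5 = 5 women. Only the pre-menopausal ones are affected; the documents do not say how many that would be.

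**6. What could pass every listed check**

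A woman eligible at screening could conceive afterwards, through contraceptive failure or a change in circumstances, or could have been pregnant too early for the screening test to show it. If she does not know, she has nothing to report at the verbal check or the history review, and no listed procedure would reveal the pregnancy before the iLet is started.

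**The case against.** The strongest reply is that the plan has several layers of protection. Criterion 6 already excludes women who are sexually active without contraception and women planning pregnancy within 12 months, and neither condition carries the two-week limit. Date of last menstrual period is taken at screening, history is reviewed at Day 1 and at crossover to confirm continued eligibility, and a daily questionnaire asks about other medical conditions. The study is two 7-day arms with about 10 completers, so an undetected pregnancy is unlikely. All of this stands, and it narrows the gap. It does not close it, because every layer after screening depends on the woman knowing that she is pregnant.

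Four stronger readings are tempting, and the documents do not support them.

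- A reader might infer that contraception is not asked for until two weeks before the study, leaving an uncovered window of 75 to 78 days. That overlooks the undated condition in the parent line of criterion 6, and it assumes that the study in 6a begins at Day 1. On the other reading the window is 0 days.
- A reader might apply the equal sex split to the maximum enrolment of 20 and count 10 women at risk. V. a. explains that the upper bound allows for volunteers excluded after screening, who never start the iLet.
- A reader might argue that an undetected pregnancy would distort the glucose and nausea results. The documents contain nothing on that effect, so it forms no part of this point.
- A reader might say the discontinuation rule cannot operate. It can, on a self-report; what it lacks is a scheduled test.

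**Conclusion.** The point holds as a gap in the visit schedule. The urine HCG that defines pregnancy in criterion 6 is listed only at screening, screening can be up to about 89 to 92 days old at Day 1, and no listed procedure after it would detect an unrecognised pregnancy before dasiglucagon starts. If the bihormonal arm comes second and the three-month limit is not reapplied at crossover, the interval to dasiglucagon could reach about 96 to 106 days.

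The number affected is small: about 5 women among the 10 expected completers, fewer if some are post-menopausal. This assumes that the anticipated equal sex split holds among completers. The probability of the event cannot be estimated from the documents. The case for acting is that the safeguard is nearly free and uses the sponsor's own test.

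The contraception wording is a separate and lesser matter. The parent line of criterion 6 and sub-item 6a need to be reconciled, but they do not show that contraception is left unrequired for any definite period.

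**What to change.** 1. Add the urine HCG already used at screening to the Day 1 and Day 7/Day 1 lists in VI. d. iv for pre-menopausal women, before the iLet is started; at minimum, before the bihormonal arm. Add it to VII. e. ii so that the result is recorded.
2. State in VI. d. i whether the three-month limit is applied again at the crossover visit, and whether re-screening repeats the HCG.
3. Reconcile the undated contraception condition in criterion 6 with the two-week window in 6a, and say whether the study in 6a begins at screening or at Day 1. The content of the requirement is for the sponsor to settle.

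**Cost.** At most two test strips per woman, so about 5 × 2 = 10 among the expected completers, at visits that subjects already attend and where blood is already drawn. No visit is added. The drawback is an occasional late exclusion, at Day 1 or at crossover, of a subject who would otherwise have continued. Items 2 and 3 are changes of wording.
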